3. OBJECTIVES AND ENDPOINTS

The study objectives and corresponding endpoints are presented in [Table 4](#).

Table 4: Study ALXN1840-WD-205 Objectives and Endpoints

Objectives	Endpoints
Treatment Period	
Primary	
To evaluate change in liver copper (Cu) concentration following treatment with ALXN1840 at Week 48 in patients with Wilson disease (WD)	Change from baseline to Week 48 in liver Cu concentration
Secondary	
To assess change in liver histopathology following treatment with ALXN1840	Change from baseline to Week 48 in steatosis, inflammation, and fibrosis
To evaluate the safety of ALXN1840 in patients with WD	Adverse events (AEs), vital signs, ECGs, clinical laboratory data, and physical examination data
To evaluate pharmacokinetics (PK) of ALXN1840	
 ALXN1840 PK profiles in plasma at Week 6 (Day 43) and Week 36 (Day 253), of which ALXN1840 PK are measured as total molybdenum (Mo) and plasma ultrafiltrate (PUF) Mo Pre-dose trough ALXN1840 concentrations in plasma at each study site visit ALXN1840 concentrations in the liver biopsy specimen.
To evaluate the effects of ALXN1840 on clinical symptoms	Change from baseline in Clinical Global Impression-Improvement (CGI-I) Scale and the Clinical Global Impression-Severity (CGI-S) Scale
Exploratory	
To explore the effects of ALXN1840 on hepatic status	Change from baseline to Week 48 in: 
 Model for End Stage Liver Disease (MELD) score Modified Nazer score
To assess changes in liver fibrosis and steatosis using non-invasive techniques	Liver stiffness by magnetic resonance (MR) elastography and transient elastography (Vibration-Controlled Transient Elastography/FibroScan), MR-proton density fat fraction (PDFF)
To explore changes in mitochondrial ultrastructure of the liver at Week 48	Change from baseline to Week 48 in mitochondrial ultrastructure by electron microscopy
To explore the change in Cu deposition in the eye at Week 48	Change from baseline to Week 48 in in Cu deposition in the eye by optical coherence tomography

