4.3. Justification for Dose

For this study, the term “dose” refers to the following:

Dosing for ALXN1840 will be initiated at 15 mg once daily, then the dose will be increased to 30 mg once daily at Week 6.

A starting dose of 15-60 mg daily was shown to have an acceptable safety profile and was effective in reducing NCC in a Phase 2 study in patients with WD (Weiss, 2017). Elevation of hepatic transaminases and/or gamma glutamyl transferase occurred in 39% of patients in the Phase 2 study and were generally associated with higher doses of ALXN1840. Elevations of

liver enzymes were detected by routine laboratory monitoring and were managed by dose reduction or treatment interruption of ALXN1840. In this study, the starting dose will be 15 mg once daily for the first 6 weeks, then the dose will be titrated up to 30 mg once daily. Elevation of liver enzymes, if occurring, and management of other laboratory abnormalities or AEs, will be managed according to [Table 6](#). Any change to dosing in response to laboratory results or AEs must be discussed with the Alexion Medical Monitor and documented in the study record. Subsequent dose increases must be approved by Alexion.

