6.6. Dose Modification

Patients will be initiated on ALXN1840 at 15 mg once daily, then the dose will be increased to 30 mg once daily at Week 6 (Day 43).

The dose should be decreased or interrupted if any of the relevant Dose Modification Criteria are met (see [Table 6](#)). Deviation from the dose modification guidelines must be agreed with the Alexion Medical Monitor. Any subsequent dose increases must be approved by Alexion.

All patients will continue to be treated with ALXN1840 in the Extension Period at the same dose they received at the last study visit in the Treatment Period and ALXN1840 administration during the Extension Period will follow the same procedures as for the Treatment Period.

In case a dose modification is necessary for ALXN1840, it will be administered as per the details in [Table 6](#).

Table 6: ALXN1840 Dose Modifications for Individual Patients

Test	Result	Conditions	Action with ALXN1840 Dosing	Changes in Safety Monitoring ^a	Re-Challenge ^b
ALT	> 5 × ↑ from baseline	ALT above reference range at baseline	Temporary interruption	Contact patient within 48 hours to arrange repeat testing Weekly repeat testing	At 15 mg QOD when ALT < 2 × ↑ from baseline.
	> 5 × ULN	ALT within reference range at baseline	Temporary interruption	Contact patient within 48 hours to arrange repeat testing Weekly repeat testing	At 15 mg QOD when ALT < 2 × ULN.
	> 2 × ↑ from baseline	ALT above reference range at baseline	Reduce dose to previous dose level if up-titration has occurred or reduce dose to 15 mg QOD if on 15 mg QD. No further dose ↑ until resolution of abnormality.	Weekly repeat testing	Not applicable.
	> 2 × ULN	ALT within reference range at baseline	Reduce dose to previous dose level if up-titration has occurred or reduce dose to 15 mg QOD if on 15 mg QD. No further dose ↑ until resolution of abnormality.	Weekly repeat testing	Not applicable.
Increased triglycerides	> 300 to 500 mg/dL or > 3.4 to 5.6 mmol/L	None	Reduce dose to previous dose level if up-titration has occurred or reduce dose to 15 mg QOD if on 15 mg QD. No further dose ↑ until resolution of abnormality.	Weekly repeat testing	Not applicable
	> 500 mg/dL or 5.6 mmol/L		Temporary interruption		At 15 mg QOD when triglyceride concentrations return to baseline

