6.2.4. Pharmacokinetic (PK) and Pharmacodynamic (PD) Sets in the Treatment Period

Patients meeting the definition for the Safety Analysis Set in the Treatment Period (Section 6.2.1) and having evaluable PK data for total Mo and/or PUF Mo (as surrogate measure for ALXN1840 PK) in plasma in the Treatment Period will be included in the PK Set in the Treatment Period.

Patients meeting the definition of Safety Analysis Set in the Treatment Period (Section 6.2.1) and having evaluable PD data for total Cu and/or PUF Cu in plasma in the Treatment Period will be included in the PD Set in the Treatment Period.

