7.2.6. Pharmacokinetic Concentration Analyses

Plasma concentrations of total Mo and PUF Mo (as surrogate measures of ALXN1840 PK) and time data will be presented in a data listing by patient. Plasma concentration data will be summarized separately by analyte, day, and time point using descriptive statistics. When calculating the geometric mean, values of 0 will be discarded.

Mean plasma concentration versus scheduled time profiles will be presented in figures on both linear and semilogarithmic scales. Individual plasma concentration versus actual time profiles will be presented similarly. The time to reach steady state will be graphically assessed by plotting mean plasma trough (pre-dose) concentration observed at the start of the dosing interval (C_{trough}) concentration versus study day in both linear and semilogarithmic scales. Additionally, time to steady state will be evaluated using stepwise testing for linear trend.

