7.2.7. Pharmacokinetic Parameter Analyses

The following plasma PK parameters, as data permit, will be calculated for total Mo and PUF Mo on Week 6 (Day 43) and Week 36 (Day 253) using noncompartmental methods with Phoenix[®] WinNonlin[®] (Certara USA Inc., Princeton, New Jersey) version 8.0 or higher or SAS[®] version 9.4 or higher (SAS Institute Inc., Cary, North Carolina), as applicable. Calculations will be based on the actual sampling times relative to the actual reference ALXN1840 dosing times recorded during the study.

- Time delay between the time of dosing and time of appearance of Mo concentration (T_{lag}) in plasma (Week 6 [Day 43] and Week 36 [Day 253])
- Maximum observed concentration (C_{max}) (Week 6 [Day 43] and Week 36 [Day 253])
- Time to maximum concentration (T_{max}) (Week 6 [Day 43] and Week 36 [Day 253])
- Trough (pre-dose) concentration observed at the start of the dosing interval (C_{trough})
- Time of the last quantifiable concentration (T_{last}) (Week 6 [Day 43] and Week 36 [Day 253])
- Observed concentration at the end of the dosing interval (C_{τ} , where $\tau = 24$ h) (Week 6 [Day 43] and Week 36 [Day 253])

- Area under the plasma concentration versus time curve (AUC) from time 0 to the last quantifiable concentration (AUC_t) (Week 6 [Day 43] and Week 36 [Day 253])
- AUC over the dosing interval (AUC_τ) (Week 6 [Day 43] and Week 36 [Day 253])
- Accumulation ratio (AR) calculated as C_{max} , C_{trough} , and AUC_τ after repeat dosing on Week 36 (Day 253) divided by those after the initial dosing on Week 6 (Day 43):
 - $C_{max,Day253}/C_{max,Day43}$
 - $C_{trough,Day253}/C_{trough,Day43}$
 - $AUC_{\tau,Day253}/AUC_{\tau,Day43}$

Additional plasma PK parameters may be calculated if deemed appropriate.

Pharmacokinetic parameters derived from plasma concentrations of total Mo and PUF Mo will be presented in data listings and summarized by analyte and day using descriptive statistics.

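### PK summaries are pooled by visit day with a 24 h dosing interval, so after Week 6 they can mix regimens; a by-dose summary is a cheap improvement

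*SAP*

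**What the plan says.** Protocol section 3 makes two plasma PK outputs secondary endpoints: "ALXN1840 PK profiles in plasma at Week 6 (Day 43) and Week 36 (Day 253") and "Pre-dose trough ALXN1840 concentrations in plasma at each study site visit".

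For concentrations, SAP 7.2.6 states: "Plasma concentration data will be summarized separately by analyte, day, and time point using descriptive statistics". For parameters, SAP 7.2.7 has results "summarized by analyte and day using descriptive statistics". The same section sets tau to 24 h for the concentration at the end of the dosing interval and lists an AUC over that interval. SAP 7.2.6 judges time to steady state from mean trough against study day, with stepwise testing for linear trend.

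The PK Set (SAP 6.2.4) takes anyone in the Safety Set "having evaluable PK data for total Mo and/or PUF Mo (as surrogate measure for ALXN1840 PK) in plasma in the Treatment Period". It sets no condition on current dose or on interruption. Neither 7.2.6 nor 7.2.7 stratifies by dose, dose-normalises, or says how to treat a sample taken while the drug is stopped.

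Under Protocol 6.6 patients start on 15 mg once daily and "the dose will be increased to 30 mg once daily at Week 6 (Day 43"). Table 6 then provides for changes. For several laboratory thresholds the action is "Reduce dose to previous dose level if up-titration has occurred or reduce dose to 15 mg QOD if on 15 mg QD". For more severe ones it is temporary interruption, with most laboratory re-challenges at 15 mg every other day. Any later increase needs sponsor approval.

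**The concern.** After Week 6 the protocol foresees four states at a PK visit: 30 mg daily, 15 mg daily, 15 mg every other day, and off drug. The SAP puts all of them into one row per visit. If dose changes occur, four things follow.

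- The Week 36 mean describes no single regimen.
- Its CV combines dose differences with between-patient variability, so it cannot be read as either.
- A falling mean trough over study days can reflect dose cuts rather than kinetics, which confuses the steady-state assessment.
- An every-other-day patient has a 48 h dosing interval, so a 24 h tau contradicts the definition of the parameters that depend on it.

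Protocol 2.2.2 says that the earlier Phase 2 study showed no clear dose-proportionality, possibly because of small numbers and variability. The dose-exposure relation is therefore open, and a table that hides dose cannot help to settle it.

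The point concerns Table 6 changes, not the planned increase at Week 6.

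**Working it through.** The documents give no figure for the PK summaries, so there is none to reproduce. They also give neither a dose-reduction rate for this trial nor a dose-exposure slope. Both are assumptions below.

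**Pooled mean.** Let p be the share of patients not on 30 mg daily at the visit, and r their exposure relative to 30 mg daily. Then

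pooled mean / 30 mg mean = (1 − p) + p·r = 1 − p(1 − r).

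For 15 mg daily, r = 0.50 if exposure is proportional to dose, √0.50 = 0.71 if it follows the square root of dose, and 1 if it is flat.

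| p on 15 mg daily | proportional | square root | flat |
|---|---|---|---|
| 10% | 1 − 0.10 × 0.50 = 0.95 | 1 − 0.10 × 0.29 = 0.97 | 1.00 |
| 20% | 1 − 0.20 × 0.50 = 0.90 | 1 − 0.20 × 0.29 = 0.94 | 1.00 |

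**CV.** Mixing two regimens adds a between-regimen SD of (1 − r)√(p(1 − p)). Under proportional exposure, even with no between-patient variability, this gives:

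- p = 10%: 0.50 × √0.09 = 0.15, divided by 0.95, a CV of about 16%.
- p = 20%: 0.50 × √0.16 = 0.20, divided by 0.90, a CV of about 22%.

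Under flat exposure it adds nothing.

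**Direction.** Suppose that patients whose dose is cut would have k times the typical exposure at equal dose. The pooled mean relative to the patients still on 30 mg is then (1 − p) + p·k·r. With p = 20% and r = 0.50:

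- k = 1: 0.80 + 0.10 = 0.90
- k = 2: 0.80 + 0.20 = 1.00
- k = 2.5: 0.80 + 0.25 = 1.05

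So the 30 mg row need not be higher than the pooled row.

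**Interruptions.** SAP 7.2.5.1 takes samples pre-dose and at 2 and 4 hours post-dose at Weeks 6 and 36. A patient not dosed on Day 253 has no post-dose samples, so interruptions do not reach the Week 36 Cmax or AUC. They can enter the pre-dose concentration and trough summaries. There, SAP 7.2.5.2 sets values below the quantification limit to 0 for the PK Set, and SAP 7.2.6 drops zeros from the geometric mean. Such a sample lowers the arithmetic mean and vanishes from the geometric one.

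**Dosing interval.** For every-other-day patients the interval is 48 h against tau = 24 h. With sampling ending at 4 h, changing tau to 48 h would not supply the missing part of the curve.

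**The case against.** The strongest reply is that the plan does not claim to estimate exposure at 30 mg. The endpoint is a profile by visit, the regimen allows doses up to 30 mg, and SAP 5.2 speaks of individualized dosing. A by-visit summary of exposure under that regimen is a legitimate descriptive target. This stands, and it is why the pooled table should remain.

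A reader might infer that the tables do understate exposure at 30 mg, and might size the effect from Protocol 4.3: "Elevation of hepatic transaminases and/or gamma glutamyl transferase occurred in 39% of patients in the Phase 2" study. With p = 39% the formula gives 1 − 0.39 × 0.50 = 0.81 on 15 mg daily and 1 − 0.39 = 0.61 if interrupted. The documents do not support this. The 39% counts enzyme elevations that ever occurred, in a study with starting doses of 15 to 60 mg. It is not a dose-reduction rate, nor the share off 30 mg on Day 253. Gamma glutamyl transferase is not a Table 6 trigger, and Protocol 2.3.1 describes transaminase elevations as usually early and reversible with dose adjustment. Nor is 39% an upper bound, since Table 6 has other triggers. The 0.61 cannot apply to Week 36 Cmax or AUC, because an undosed patient has no post-dose profile.

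The SAP also provides concentration and parameter listings, individual profiles, and a listing of dose and frequency with dates (7.2.6, 7.2.7, 7.3.1). A reader could link these by hand for about 28 patients, but the listings do not change what the summaries say. Protocol 9.4.3 allows for a separate PK/PD analysis plan. It is not among the documents, so it can be neither credited nor ruled out.

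Finally, a by-dose table does not yield unbiased exposure at 30 mg, because patients still on that dose are selected for tolerability. This stands too, and the table should say so.

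**Conclusion.** The gap is real, and its consequences depend on how many patients change dose. As written, the SAP pools whatever regimens are present at each visit and applies a 24 h interval to patients whose interval is 48 h. The mis-definition for every-other-day patients follows from the text alone. The effect on means and CVs rests on an assumed share of reduced patients and an assumed dose-exposure slope.

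Because 30 mg is the highest level, a pooled mean below the 30 mg mean is the expected direction if exposure rises with dose. With 10% to 20% of patients on 15 mg daily, the illustrated ratio runs from 0.90 to 1.00. It could also exceed 1 against the observed 30 mg group if patients with high exposure are the ones whose dose is cut. A firm statement of understatement is therefore not justified.

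The affected results are descriptive secondary PK summaries. The primary test and its power are untouched. This is a cheap improvement of minor severity.

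**What to change.** In SAP 7.2.6 and 7.2.7:

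- Add summaries of concentrations and parameters by actual dose and regimen at the visit, with n per regimen. Use the dosing dates and doses already recorded under Protocol 6.4 and listed under SAP 7.3.1.
- List samples taken during an interruption, and exclude them from the trough and steady-state summaries.
- Omit the tau-based parameters for every-other-day patients.
- Keep the pooled by-visit table.
- State that the by-dose rows are descriptive, because patients remaining on 30 mg are selected for tolerability.

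The cost is SAP wording and one more by-variable in the PK tables. No new data are needed and dosing does not change. The downside is small cells: with 24 completers and 20% off 30 mg, 24 × 0.20 ≈ 5 patients would be spread over the other rows.

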7.2.8. Pharmacodynamic and Biomarker Concentration Analyses

Individual plasma concentration data for measured total Cu, PUF Cu, cNCC/ $NCC_{corrected}$, dNCC, LBC, Cp, and CpC (and Mo and Cu in TPCs if measured) will be summarized separately for each scheduled sampling time using descriptive statistics. When calculating the geometric mean, values of 0 will be discarded. Individual concentration data will be presented in data listings. Individual concentration versus actual time profiles will be provided. Additionally, mean concentration versus nominal time profiles will be provided. Note that the measured, change from Baseline, and percent change from Baseline concentration data for PD and biomarker will be listed, summarized, and presented graphically on linear scales. Similar analysis plan will also be performed for 24-hour urine Cu/Mo/creatinine when applicable.

The dNCC are obtained by inductively coupled plasma mass spectrometry after immunocapture and removal of ceruloplasmin. The daily mean AUEC of dNCC from 0 to 48 weeks, denoted as $AUEC_{0-48w}$, will be calculated using the linear trapezoidal rule.

$$AUEC_{0-t_n} = \sum_{i=1}^n \frac{c_{i-1} + c_i}{2} (t_i - t_{i-1})$$

where, n = number of measured timepoints.

The AUEC is then divided by the number of days to yield $AUEC_{0-48w}$. $AUEC_{0-48w}$ of dNCC will be summarized using descriptive statistics including geometric mean and geometric %CV.

In addition to dNCC, cNCC will be calculated by subtracting the amount of Cu bound to Cp from the total plasma Cu level:

$$cNCC [\mu mol/L] = \frac{\text{Total plasma Cu } [\mu g/L] - (3.15 \times Cp [mg/L])}{63.5 [\mu g/\mu mol]}$$

For patients dosed with ALXN1840, there is also Cu bound in the tetrathiomolybdate-Cu-albumin TPC, which is addressed by the NCC correction method:

$$NCC_{corrected} = (\sqrt{cNCC} - 0.993\sqrt{Mo})^2$$

In the calculation of cNCC and $NCC_{corrected}$, the following adjustments will be made:

- Cu values < LLOQ are set to missing and cNCC will not be derived.
- Cp values < LLOQ are set to 0.
- Mo values < LLOQ are set to 0.
- Negative cNCC values are not utilized and $NCC_{corrected}$ will not be derived.
- $NCC_{corrected}$ will be set to 0 when $0.993\sqrt{Mo} > \sqrt{cNCC}$.

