7.2.4. Other Efficacy Analyses

All exploratory analyses will be performed using the FA Set in the Treatment Period.

Assessment for each exploratory endpoint will be summarized for Baseline and post-baseline visits by descriptive statistics. Change from Baseline and percent change from Baseline (for plasma total and PUF Cu, cNCC, dNCC, LBC, Cp, and CpC only) will also be summarized for each post-baseline visits. In addition, following analyses will be done.

Endpoints with continuous outcome, which are measured multiple times between Baseline and Week 48, will be analyzed using the MMRM in the same manner as of CGI-S. Details of the MMRM can be referred to in Section [7.2.2](#).

- MELD
- Modified Nazer
- Plasma total and PUF Cu
- cNCC
- dNCC
- LBC
- Cp and CpC
- EQ-5D
- SF-36
- CLDQ
- BPRS-24
- FIB-4
- 24-hour Urine Cu/Mo/creatinine

For plasma total and PUF Cu, cNCC, dNCC, LBC, Cp, and CpC, additional MMRM model will be performed on percent change from Baseline.

For all exploratory endpoints with multiple measurements between Baseline and Week 48, the following plots will also be provided: mean and 95% CI plot over time, and spaghetti plot for patient level data over time.

For endpoints with continuous outcome that are only measured at Baseline and Week 48, a paired sample t-test on Baseline and Week 48 assessment values will be performed when data are available.

- Liver stiffness by MRE (kPA)
- Liver stiffness by transient elastography (kPA)
- Steatosis by MR-PDFF (percentage)
- Liver metals concentrations obtained from liver biopsy specimen

For endpoints with ordinal outcomes that are only measured at Baseline and Week 48, a Wilcoxon Signed-rank test will be used to compare Baseline versus Week 48 assessment values.

- TSQM-9
- UWDRS

The reference SAS code for a paired sample t-test and a Wilcoxon Signed-rank test can be found in Section 9.5.

For mitochondrial ultrastructure by electron microscopy and Cu deposition in the eye by optical coherence tomography, only by-patient listings will be provided.

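### SAP 7.2.8 deletes negative cNCC values but keeps slightly positive ones, with NCC-corrected floored at 0, which biases mean cNCC and mean NCC-corrected upward at any visit where negatives occur

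*SAP*

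**What the plan says.** SAP 7.2.8 states that "cNCC will be calculated by subtracting the amount of Cu bound to Cp from the total plasma Cu level". The formula is cNCC = (total plasma Cu − 3.15 × Cp) / 63.5, in µmol/L. Copper held in the drug's albumin complex is then removed by NCC-corrected = (√cNCC − 0.993√Mo)².

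The same section lists adjustments for both calculations:
- Negative result: "Negative cNCC values are not utilized", and NCC-corrected is then not derived.
- Small non-negative result: cNCC stands, and NCC-corrected "will be set to 0 when" 0.993√Mo exceeds √cNCC.
- Low ceruloplasmin: "Cp values < LLOQ are set to 0".

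Absolute and percent change in cNCC to Week 48 are exploratory endpoints (Protocol Section 3, Table 4; SAP 5.1.3). SAP 7.2.4 summarizes "Change from Baseline and percent change from Baseline (for plasma total and PUF Cu, cNCC, dNCC, LBC, Cp, and CpC only") and fits an MMRM to each. NCC-corrected is not on the MMRM list; it is summarized descriptively under 7.2.8. Under SAP 9.4.6 a change is missing when either of its two values is missing.

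**The concern.** cNCC is a difference of two measured quantities. When the true value is low, error in either assay can push the result below 0. Such a result is imprecise, but it still indicates a low value. Deleting it makes missingness depend on the value itself, and an MMRM does not correct for that.

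The two rules also conflict at the boundary. A cNCC just above 0 gives the lowest possible NCC-corrected, namely 0. A cNCC just below 0 gives no NCC-corrected at all. SAP 7.2.5.2 treats other low pharmacodynamic concentrations differently: values below the LLOQ stay in the summaries, at the LLOQ in the FA Set or at 0 in the PD Set. That rule does not address negative derived values.

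At stake are the reported levels of cNCC and NCC-corrected and, depending on when negatives occur, the change in cNCC. Neither document plans a count of the deleted values or a sensitivity analysis under another rule.

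**Working it through.** No sample size, power or alpha in the plan depends on this rule, so there is no stated figure to reproduce.

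**1. The boundary (SAP 7.2.8 formulas; Cu and Cp chosen for illustration).** Take Cu = 300 µg/L.
- Cp = 95 mg/L: (300 − 299.25)/63.5 = +0.012. cNCC is kept. NCC-corrected is 0 whenever 0.993² × Mo > 0.012, that is, for Mo above about 0.012 in the formula's units.
- Cp = 96 mg/L: (300 − 302.4)/63.5 = −0.038. Both measures are lost.

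**2. Direction of the bias in levels.** Every retained cNCC is at least 0, so removing negatives always raises the arithmetic mean. NCC-corrected is never negative, so omitting cases that belong at its floor raises its mean whenever any retained value is positive. Neither statement needs a distribution. Example with cNCC = −0.6, 0.1, 0.8, 1.5, 2.3 and Mo = 0.4:
- Mean cNCC: SAP rule 4.7/4 = 1.175; floor at 0, 4.7/5 = 0.94; all values 4.1/5 = 0.82.
- Mean NCC-corrected: SAP rule 0.304; negative carried as 0, 0.243.

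**3. Size of the bias in levels.** The documents give no mean, SD or share of negatives for cNCC. Assume a normal distribution with mean m and SD s, and write a = m/s. Then:
- share negative = 1 − Φ(a)
- rise under the SAP rule = s·φ(a)/Φ(a)
- rise under a floor at 0 = s·φ(a) − m·[1 − Φ(a)]

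The value 0.8 is the lower limit of the cNCC reference range in SAP 7.1.3.2 (0.8 to 2.3 µmol/L); 1.5 is near its middle.

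| m | s | negative | rise, SAP rule | rise, floor at 0 |
|---|---|---|---|---|
| 1.5 | 0.7 | 2% | 0.03 (2%) | 0.004 |
| 1.5 | 1.0 | 7% | 0.14 (9%) | 0.03 |
| 0.8 | 0.7 | 13% | 0.17 (21%) | 0.04 |
| 0.8 | 1.0 | 21% | 0.37 (46%) | 0.12 |
| 2.0 | 0.5 | about 0% | 0.00 | 0.00 |

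At m = 0.8, 13–21% of 28 patients is about 4–6 values per visit.

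Mean NCC-corrected under the SAP rule is 1/(1 − share negative) times the mean with negatives carried as 0, whatever Mo is. At 7% negative the factor is 1/0.93 = 1.07. A simulation with m = 1.5, s = 1.0 and fixed Mo of 0.25, 0.5 or 1.0 gave the same 1.07 each time.

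**4. Change from Baseline.** A simulation used complete pairs with a shared patient component (SD 0.6) and independent visit variation (SD 0.8), so the total SD was 1.0.
- Mean 2.0 falling to 0.8: true change −1.2, estimated −0.99, with 78% of pairs kept.
- Mean 0.8 rising to 2.0: true change +1.2, estimated +0.99.
- Mean 1.0 at both visits: no bias.

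**5. Baseline.** Table 1 in Protocol Section 1.3 schedules plasma PK/PD samples on Day 1 and none at Screening. Baseline is the last valid value before the first dose (SAP 9.4.5), so a negative Day 1 cNCC normally has no replacement. That patient then has no change in cNCC or NCC-corrected at any visit.

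**The case against.** **The bullet can be read more narrowly.** NCC-corrected needs √cNCC, which does not exist for a negative value, so the rule might only bar negatives from the correction. The copper bullet is more explicit about deletion ("Cu values < LLOQ are set to missing and cNCC will not be derived"). This reading is strained: the list covers the calculation of both cNCC and NCC-corrected, and the negative-value bullet has two separate clauses. No other section brings negatives back into the cNCC analyses.

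**Keeping raw negatives everywhere would do harm.** This stands. Percent change divides by Baseline (SAP 7.2.5.3), so a Baseline of −0.1 and a later value of 1.0 give −1100% for what is a rise. A Baseline floored at 0 leaves percent change undefined. Geometric means do not exist for negative values, and the SAP already says "When calculating the geometric mean, values of 0 will be discarded". The fix must treat these two quantities separately.

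**The size rests on assumptions.** This also stands. A normal distribution with SD 0.7–1.0 puts mass below 0 by construction. On treatment, cNCC includes copper in the drug's albumin complex, which pushes it up, so the low-mean cases are not shown to apply after Baseline. At Baseline low values are plausible, because every patient has had at least a year of copper-lowering therapy (Protocol 5.1).

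**Stronger readings that the documents do not support.** A reader might infer that the patients with the least copper drop out of the trial's analyses. What is lost is single patient-visit values, unless Day 1 is negative, and then only the cNCC and NCC-corrected changes go. A negative value can also come from assay error alone. A reader might also infer that the change in cNCC must be biased. That depends on when negatives occur, and the bias cancels when the distribution is the same at both visits.

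**Conclusion.** The concern holds for levels. The SAP rule removes values because they are low, and it raises mean cNCC and mean NCC-corrected at any visit with negatives. The direction is certain; the size is not. With an assumed normal distribution and SD 0.7–1.0 µmol/L, mean cNCC rises by about 0.03–0.14 at a true mean of 1.5 and by 0.17–0.37 at 0.8. If negatives are rare, nothing material happens.

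Bias in change from Baseline arises only if negatives are unequally frequent at Baseline and the later visit. In the simulated cases it shrank a change of 1.2 to 0.99.

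The consequence is limited. cNCC is exploratory and NCC-corrected is only described. The primary liver Cu analysis does not use cNCC, and dNCC and LBC have their own analyses, which do not depend on this subtraction. The rule is still worth changing, because it is internally inconsistent and cheap to repair.

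**What to change.** Amend the adjustment list in SAP 7.2.8, with a matching line in 7.2.4:

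1. Set NCC-corrected to 0 when cNCC is negative, in line with its existing floor.
2. In the cNCC level summaries and the absolute-change MMRM, floor negative cNCC at 0 instead of deleting it. Alternatively, keep it as calculated and use the other rule as a sensitivity analysis. A floor leaves some upward bias (0.04–0.12 at a true mean of 0.8 under the same assumptions), but much less than deletion.
3. Leave percent change missing when Baseline cNCC is 0 or below, and leave non-positive values out of geometric means.
4. Report the number of negative cNCC values at each visit.

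The cost is a few lines of SAP text and no new data. The downside is that some zero or negative values will appear in the summaries, and percent change stays unavailable for patients with a non-positive Baseline.
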